2.1.2 Secondary Analysis

Analysis set: Full analysis set
Per protocol set

Analysis variables: Change in HbA1c at the end of Treatment Period I from Week 0

Analysis methodology: The analysis (1) will be performed in the “full analysis set” and (2) in the “per protocol set” for the above analysis variables.

- (1) Summary statistics and the two-sided 95% CI for the mean will be calculated for each treatment group, as well as the intergroup difference in the mean between treatment groups (SYR-472 25 mg/SYR-472 25 mg group – placebo/SYR-472 25 mg group) and the two-sided 95% CI.
- (2) In addition, the same analyses as 2.1.1 Primary Analysis and 2.1.2 Secondary Analysis (1) will be performed to evaluate the robustness of the results in terms of a sensitivity analysis.

2.2 Secondary Endpoints and Analysis Methodology

2.2.1 HbA1c, Fasting Blood Glucose, Glycoalbumin

Analysis set:	Full analysis set
Analysis variables:	HbA1c Fasting blood glucose Glycoalbumin
Visits:	HbA1c Weeks -6, -2, 0, 2, 4, 8, 12, 16, 20, 24, 28, 32, 36, 40, 44, 48, 52, at the end of Treatment Period I, and at the end of Treatment Period II Fasting blood glucose Weeks -6, 0, 2, 4, 8, 12, 16, 20, 24, 28, 32, 36, 40, 44, 48, 52, 54, at the end of Treatment Period I, and at the end of Treatment Period II Glycoalbumin Weeks -6, -2, 0, 2, 4, 8, 12, 16, 20, 24, 28, 32, 36, 40, 44, 48, 52, 54, at the end of Treatment Period I, and at the end of Treatment Period II
Analysis methodology:	
The following analyses (1) and (2) will be performed for the above analysis variables. Also, the following analysis (3) will be performed for HbA1c.
 
For the mean and standard deviation plot, a plot until Treatment Period I and a plot for the entire study will be created, respectively, but the plot for the entire period will not be output at Week 54 or at the end of Treatment Period I.
 
(1) Summary statistics and the two-sided 95% CI for the mean will be calculated for each visit and the mean and standard deviation plot by treatment group will be prepared. Also, the intergroup difference in the mean between treatment groups (SYR-472 25 mg/SYR-472 25 mg group – placebo/SYR-472 25 mg group) and the two-sided 95% CI will be calculated for each visit during the Screening and Treatment Period I.
 
(2) The same analysis as the above (1) will be performed for changes from Week 0 at each visit after Treatment Period I.
 
(3) For the proportions of subjects who achieved an HbA1c less than 6.0%, 7.0%, or 8.0% at the end of Treatment Period I and Treatment Period II, the proportions and the two-sided 95%

CIs will be calculated for each treatment group, and the intergroup difference in the proportions between treatment groups (SYR-472 25 mg/SYR-472 25 mg group – placebo/SYR-472 25 mg group) and the two-sided 95% CIs will be calculated at the end of Treatment Period I. In the analysis of each proportion, subjects who did not achieve the relevant target HbA1c at Week 0 will be included in the analysis.

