5.0 STUDY OBJECTIVES AND ENDPOINTS

5.1 Objectives

To evaluate the efficacy and safety of SYR-472 when administered at a dose of 25 mg once weekly using placebo as a control in patients with type 2 diabetes mellitus complicated by severe renal impairment or end-stage renal failure and with inadequate glycemic control despite diet and/or exercise therapy (if any) or despite treatment with 1 antidiabetic drug in addition to diet and/or exercise therapy (if any); and to evaluate the long-term safety and efficacy of SYR-472 when administered at a dose of 25 mg once weekly in patients with type 2 diabetes mellitus complicated by severe renal impairment or end-stage renal failure.

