- For subjects who are not using any other antidiabetic drug in Treatment Period I (those who are only treated with the study drug), the use of 1 new oral hypoglycemic drug* is allowed at Week 16 of the treatment period and thereafter.

*: Any 1 of the following medications: metformin, repaglinide, acarbose, miglitol, or voglibose

(2) Insulin Preparations

For subjects who are receiving insulin preparations at the start of the screening period (Week -6) and continue to receive in the study period, insulin preparations should be administered as specified below.

• Type of Insulin Preparation

Any 1 of the mixed (rapid-acting or ultrarapid insulin containing no more than 30% of volume), intermediate-acting, or long-acting soluble insulin preparations should be used alone, and should not be changed throughout the study period.

• Daily Dose (Unit) of Insulin Preparation

1) Screening Period

The daily dose (unit) of insulin preparation should be 40 units/day or less at the start of the screening period (Week -6), and the dose and regimen should not be changed during the screening period (for subjects on hemodialysis who receive different daily doses [unit] of insulin preparation on days of hemodialysis and on other days, each dose and regimen of insulin preparation should not be changed).

2) Treatment Period I

The dose and regimen of insulin preparations at the start of the screening period (Week -6) should be maintained and no changes will be allowed, in principle.

However, the investigator or sub-investigator should consider reduction or increase in the daily dose (unit) of insulin preparation if the criteria described below are met. After dose reduction or increase, the unit after reduction or increase should be continued.

Even if reduction in the daily dose (unit) of insulin preparation results in the discontinuation of insulin use, the study may be continued. If increase in the daily dose (unit) of insulin preparation results in a dose exceeding 40 units/day on a continuing basis, the investigator or sub-investigator should determine whether the study should be continued or discontinued, with respect to the safety of the subject.

Criteria for dose reduction: If either criterion (i) or (ii) described below is met, the daily dose (unit) of insulin preparation may be reduced from the unit administered at the start of the screening period (Week -6) by up to 4 units (regardless of the number of changes).

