- ii) Hypoglycemia is suspected since the subject has had 2 or more consecutive self-monitoring blood glucose values of ≤ 70 mg/dL, and the investigator or sub-investigator considers that the risk of developing hypoglycemia is high.

Criteria for dose increase: If a subject has had 2 or more consecutive self-monitoring blood glucose values of >200 mg/dL and the investigator or sub-investigator considers that the increase of insulin preparation is necessary in view of the safety of the subjects, whether or not to increase the daily dose (units) of insulin preparation should be considered.

<Justification of Restricted Medications>

For oral hypoglycemic drugs, changes in the basic treatment are prohibited in the screening period and Treatment Period I with respect to the possible influence on the efficacy and safety evaluation of SYR-472. In Treatment Period II and the follow-up period, changes in the dose or regimen as well as discontinuations and interruptions are allowed due to ethical considerations on the state of glycemic control for patients with type 2 diabetes mellitus complicated by renal impairment during the 54-week study period. In addition, for subjects who do not receive any other antidiabetic drug in Treatment Period I and still show inadequate glycemic control after 4 weeks following entry into Treatment Period II (Week 16 of the treatment period or thereafter), 1 oral hypoglycemic drug only may be additionally administered at the discretion of the investigator and sub-investigator.

For insulin preparations, changes in the daily dose (unit) are permitted according to the fixed criteria for dose reduction or increase, if the investigator or sub-investigator considers it necessary from the perspective of the safety of the subject.

3. Other medications

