9.1.3 Antidiabetic Drugs Administered During the Study

1. Screening Period

CONFIDENTIAL

For antidiabetic drugs administered at the start of the screening period (Week -6) and concomitantly used during the study period, the drug name, type (for insulin preparations), and daily dose of antidiabetic drugs used at the start of the screening period (Week -6) and concomitantly used during the study will be recorded in the eCRF.

2. Treatment Period I

For antidiabetic drugs administered at the start of the screening period (Week -6) and concomitantly used during the study period, the drug name, type (for insulin preparations), and daily dose of antidiabetic drugs used at the start of the screening period (Week -6) and concomitantly used during the study period will be recorded in the eCRF.

In case concomitant use of other antidiabetic drugs in addition to an antidiabetic drug used at the start of the screening period (Week -6) is judged to be appropriate, the investigator or sub-investigator should record the reason for the judgment in the eCRF according to the following categories:

- Combination therapy is expected to be more effective.
- Development of AEs due to dose increase is concerned.
- The maximum dose has already been administered.
- Others

3. Treatment Period II

For subjects who do not receive 1 antidiabetic drug other than the study drug in Treatment Period I and start the administration of 1 new oral hypoglycemic drug from Week 16 of the Treatment Period II (or thereafter), the drug name, daily dose, date of the start and end of administration, will be recorded in the eCRF.

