9.1.7 Documentation of Concomitant Medications

Concomitant medication is any drug given in addition to the study drug and antidiabetic drugs. These may be prescribed by a physician or obtained by the subject over the counter. Concomitant medication is not provided by Takeda. At each study visit, subjects will be asked whether they have taken any medication other than the study drug (including vitamin supplements, over-the-counter medications, and herbal preparations) used from the start of the screening period (Week -6) through the end of the study, and the drug name, route of administration, dates of the start and end of administration, and purpose of use must be recorded in the eCRF.

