13.3 Determination of Sample Size

Randomized subjects: 53 subject per group, 106 in total

(Changed as of 12 September 2016)

<Justification of sample size>

In Study CCT-002, the intergroup difference (two-sided 95% CI) in the mean change in HbA1c (JDS value) at the end of the treatment period (value at the end of the treatment period - value at the end of the screening period) between the SYR-472 100 mg group and placebo group was -0.56 ([-0.753, -0.367])%. In the same study, the standard deviation of the change in HbA1c (JDS value) at the end of the treatment period (value at the end of the treatment period - value at the end of the screening period) for each treatment group ranged from 0.523% to 0.628%.

In this study, which will administer SYR-472 at a dose of 25 mg once weekly to patients with type 2 diabetes mellitus complicated by severe renal impairment or end-stage renal failure, the intergroup difference in the mean change in HbA1c at the end of Treatment Period I from the end of the screening period (Week 0) between the SYR-472 25 mg group and placebo group is assumed to be -0.40%, given that the efficacy of SYR-472 25 mg in this study is similar to that of SYR-472 100 mg administered once weekly to patients with type 2 diabetes mellitus not complicated by renal impairment. The common standard deviation in each treatment group is assumed to be 0.80%.

CONFIDENTIAL

Based on these assumptions, 86 subjects per group will be required to provide a 90% power in a two-sample t-test with a significance level of 5% (two-sided). Therefore, the sample size was set at 90 as randomized subjects per group at the start of the study allowing for the possibility that there exit some subjects whose primary endpoint cannot be evaluated.

However, achievement of the sample size as originally planned at the start of the study was found difficult because there were more than expected numbers of candidate subjects who did not provide consent and who dropped out during screening after providing consent for the study. It was therefore decided to change some of the inclusion and exclusion criteria for this study. After these changes, the ultimate number of subjects randomized and evaluable for the primary endpoints are expected to be around 53 and 51, respectively, per group.

Assuming the number of subjects per group as 51 under these assumptions, the study will provide a 70.6% power in a two-sample t-test with a significance level of 5% (two-sided).

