4 SIGNIFICANCE LEVEL AND CONFIDENCE COEFFICIENT

- Significance level: 5% (two-sided tests)
- Confidence coefficient: 95% (two-sided)

History of Revision (version management)

Version	Date	Prepared/modified by	Comments
First Version	16 April 2018	PPD	Preparation of first version
Second Version	12 June 2018		Preparation of second version

[Appendix 1] SYR-472-3003 Comparison Table for Changes

Page	Existing Text	Revised Text	Rationale for Changes
18	
1.2.1 Distribution of Baseline Demographics
 
Rapid-acting insulin secretagogues [Yes]
 
...
 
α-glucosidase inhibitors [Yes]
 
...
 
Insulin preparations [Yes]
 
Mixed [Yes]
 
Intermediate-acting [Yes]
 
Long-acting soluble [Yes]
	
1.2.1 Distribution of Baseline Demographics
 
Rapid-acting insulin secretagogues [Yes, No]
 
Details of rapid-acting insulin secretagogues
 
...
 
α-glucosidase inhibitors [Yes, No]
 
Details of α-glucosidase inhibitors
 
...
 
Insulin preparations [Yes, No]
 
Types of insulin preparations [Mixed, intermediate-acting, Long-acting soluble]
	Adjustment of descriptions and changes in the contents of distributions as a result of reexamination of contents of distributions
19	
1.2.1 Distribution of Baseline Demographics
 
HbA1c (%) (Week 0)
 
[Min\leq - <8.0, 8.0\leq - \leqMax]
	
1.2.1 Distribution of Baseline Demographics
 
HbA1c (%) (Week 0)
 
[Min\leq - <7.0, 7.0\leq - \leqMax]
 
[Min\leq - <8.0, 8.0\leq - \leqMax]
	Addition of distributions as a result of reexamination of contents of distributions
20	
1.2.4 Concomitant Antidiabetic Drugs
 
Permitted in the Study
 
Any change in doses of antidiabetic drugs that are being used at Week -6 and will be concomitantly used during the study period in Treatment Period II
	
1.2.4 Concomitant Antidiabetic Drugs
 
Permitted in the Study
 
Any change in antidiabetic drugs that are being used at Week -6 and will be concomitantly used during the study period in Treatment Period II
	Adjustment of descriptions to clarify the contents of distribution

Page	Existing Text	Revised Text	Rationale for Changes

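### SAP 2.2.1 summarises Period II glycaemic results regardless of permitted treatment intensification, does not say so, and offers no companion summary without it

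*SAP*

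**What the plan says.** Protocol 5.1 gives two aims. The second is "to evaluate the long-term safety and efficacy of SYR-472 when administered at a dose of 25 mg once weekly" in this renally impaired population. Period II is open-label, and the placebo group switches to SYR-472 at Week 12 (Protocol 6.1).

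Protocol 7.3 relaxes the background-therapy rules in Period II:

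- For subjects using no other antidiabetic drug in Period I, "the use of 1 new oral hypoglycemic drug* is allowed at Week 16 of the treatment period and thereafter". The justification in the same section ties this to control that is still inadequate four weeks into Period II.
- For existing oral drugs, "changes in the dose or regimen as well as discontinuations and interruptions are allowed due to ethical considerations on the state of glycemic control".
- Insulin increases are considered after two or more consecutive self-monitored values above 200 mg/dL. The 4-unit limit that applies in Period I is not stated for Period II.

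SAP 2.2.1 summarises HbA1c, fasting glucose and glycoalbumin in the full analysis set by visit to Week 52 and at the end of Period II. For change from baseline it says "The same analysis as the above (1) will be performed for changes from Week 0 at each visit after Treatment Period I". It also gives the proportions below HbA1c 6.0, 7.0 and 8.0% at the end of each period, among subjects not already at that target at Week 0. No condition refers to added or changed therapy. SAP 1.2.4 separately counts subjects with a newly added oral drug or a change in existing antidiabetic drugs in Period II.

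**The concern.** The two upward steps, the new oral drug and the insulin increase, are prompted by poor glycaemic control, which is what these tables measure. A subject whose control is inadequate on SYR-472, who then receives a second drug and ends below 7.0%, enters the end-of-Period-II table as a responder. The Week 52 mean likewise includes values obtained after the step. A waning effect of SYR-472 could be partly masked, and nothing planned would show whether it was: SAP 1.2.4 says how many subjects had a change but does not connect that to any efficacy value.

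What is at stake is the reading of the long-term efficacy objective, since these tables are the planned glycaemic evidence for it after Week 12. The primary comparison is made at the end of Period I, before these Period II changes are permitted.

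**Working it through.** **1. The plan's own figures.** No sample size or precision is stated for Period II. The Period I figures in Protocol 13.3 reproduce with a two-sample t-test (two-sided 5%, difference 0.40, SD 0.80): 86 per group gives 90.3% power, and 51 per group gives 70.56% against the stated 70.6%. They are not affected by this point.

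**2. Is there a rule elsewhere in the SAP?**

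- Time windows: values are selected by study day and by days from dosing. The end-of-Period-II HbA1c is the evaluable value closest to Day 7 after the last SYR-472 tablet, so in a subject who intensified and stayed on treatment it normally follows the step.
- 2.4.2: removes missing and ineligible data and names no therapy-change rule.
- 2.1.2 and 2.4.8: the per-protocol and subgroup analyses concern the Period I endpoint only.
- 1.2.4: counts changes and is not linked to 2.2.1.

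So 2.2.1 is in effect a summary regardless of therapy changes, though it is not labelled as one.

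**3. Size for the mean.** Shift = (share intensified) × (HbA1c effect of intensification). The documents give neither input, so both ranges are assumptions: 10–40% and 0.3–0.8 percentage points.

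- Low: 0.10 × 0.3 = 0.03 points
- Middle: 0.20 × 0.5 = 0.10 points
- High: 0.40 × 0.8 = 0.32 points

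Two yardsticks, for scale only. Protocol 13.3 assumes a 0.40-point drug effect, so the range is 0.03/0.40 = 7.5% to 0.32/0.40 = 80% of it. That 0.40 is a between-group difference at the end of Period I, whereas the shift is in a within-group change from Week 0. Second, if the planning SD of 0.80 also held at Week 52, the 95% confidence half-width for one group's mean change would be 0.225 at n = 51 and 0.256 at n = 40. The assumed shift therefore runs from negligible to larger than the sampling error.

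**4. Size for the responder proportions.** Let *m* be the subjects not at a given target at Week 0, *r* those at target at the end of Period II, and *q* those among *r* who intensified first. The plan reports *r/m*. Counting intensified subjects as non-responders gives (*r* − *q*)/*m*. The difference, *q/m*, is at most the intensified share of those *m* subjects. That share may differ from the share in the full analysis set.

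**5. Direction.** Protocol 7.3 also allows oral drugs to be reduced, stopped or interrupted, and insulin to be reduced for hypoglycaemia. Those changes would tend to raise HbA1c. Step 3 describes intensification alone, not the net of all changes.

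**6. Can the changes be identified?** For Period II, Protocol 9.1.3(3) lists eCRF entries for subjects who "start the administration of 1 new oral hypoglycemic drug from Week 16 of the Treatment Period II (or thereafter"), including start and end dates. It lists nothing for changes to existing oral drugs or insulin. Section 9.1.7 opens with "Concomitant medication is any drug given in addition to the study drug and antidiabetic drugs", yet then has sites ask about every medication apart from study drug. Its listed items include dates but not dose, so a dose increase could not be read from them. SAP 1.2.4 nonetheless reports these changes. It also defines its populations by antidiabetic use at Week -16, as does SAP 1.3.2. No visit takes place then (the first is Week -6), and the 1.2.4 variables refer to Week -6.

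**The case against.** Several stronger readings are tempting, and the documents do not support them.

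- *That the SAP treats background therapy as fixed.* It does not. SAP 1.2.4 counts additions and changes by group, and its Period II runs to 20 days after the last dose, matching the upper end of the HbA1c windows. The fair criticism is the missing label and companion table.
- *That therapy changes are why long-term efficacy cannot be attributed to SYR-472.* Everyone receives SYR-472 in Period II, so change from Week 0 would lack a concurrent control even on unchanged therapy. Intensification is an additional limit. SAP 2.2.1 makes no between-group comparison in Period II, and SAP 2.4.5 treats all non-primary results as supportive or exploratory.
- *That every permitted change follows poor control, so results are always flattered.* Oral drugs may be changed or stopped without that condition, and reductions work the other way. Intensification is also restricted: one new oral drug only, only in subjects on none in Period I, with new insulin and several drug classes listed as excluded.
- *That dates and doses are not captured.* The eCRF is not available here. The supportable statement is that the protocol text does not list them.

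Two further cautions stand. The Handling Rules for Analysis Data are also unavailable and could make some of these values ineligible, although the changes are permitted and nothing supplied suggests it. And the phrase about visits after Treatment Period I may mean from Period I onward; on either reading the visit list runs to Week 52.

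None of this removes the core point. The plan states no handling for post-intensification values in the tables that serve a named objective.

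**Conclusion.** The point holds in a limited form. The Period II glycaemic summaries and responder proportions include values obtained after permitted, control-driven intensification. The SAP does not say so and plans nothing that would show how much it matters. Under assumed inputs (10–40% intensified, 0.3–0.8 points each) the mean shifts by 0.03–0.32 points towards a better result, before any offset from reductions or stops. A responder proportion can rise by at most the intensified share of its denominator. The documents cannot narrow these ranges. The primary Period I analysis is unaffected. This is an inexpensive improvement that should be made; it does not defeat the study's objective.

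**What to change.** In SAP 2.2.1, keep the all-data summaries and state that they include values regardless of therapy changes. Add for Period II:

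- (a) the same visit-wise summaries with values after the first added antidiabetic drug or first dose increase set aside;
- (b) the end-of-Period-II proportions with such subjects counted as non-responders.

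In Protocol 9.1.3(3), confirm or add eCRF recording of the date and daily dose of every Period II change to existing oral drugs and insulin; SAP 1.2.4 needs this too. Reconcile Week -16 in SAP 1.2.4 and 1.3.2 with the Week -6 used in the 1.2.4 variables.

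The cost is a few descriptive tables and possibly one eCRF item. No treatment rule changes. Table (a) will have fewer late values, from a selected group who did not need intensification, so it does not isolate the effect of SYR-472. It is supportive only and belongs beside the all-data table.
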